There is also a very small risk that the subject could have an allergic reaction to the drug in either product. If this occurs in the ED, the RA will notify the treating physician at once. If this occurs after discharge, the subject will be directed to seek immediate medical attention. Symptoms of an allergic reaction include rash, itching, swelling, dizziness, and trouble breathing.

Risks Associated with Breath Collection

Breath Collection - Subjects will have breath samples taken to measure CO to verify clinical equivalence of treatment groups at baseline. Testing will be performed by a trained research associate with the Bedfont Micro+® breath CO monitor (Bedfont Scientific Ltd., Rochester, UK). There are no known risks associated with this test. Subjects exhale into a disposable plastic sterile straw attached to the monitor; there should be no risk of infection.

Risks Associated with Rating Scales and Assessments

Other risks from the rating scales and assessments, self-reports, and interviews are not beyond usual research procedures. Research assessments are all non-invasive, and should add no risk. The major disadvantages are the time taken to complete them and possible breach of confidentiality. Our past experience with these measures indicates that they are acceptable to subjects. Any potential risks (e.g., discussion of upsetting events), however, will be minimized through the use of a trained, experienced Research Associates, supervised by Drs. [name] and [name] for screening, intervention, and appropriate referrals. In addition, the Yale-New Haven ED has an onsite, adjacent Crisis Intervention Unit (CIU) staffed by attending and resident psychiatrists 24 hours each day which can be accessed if necessary. All adverse events will be immediately reported to the PI by research staff.

Risks Associated with Texting

The text messaging program will serve as a stand-alone health education program for quitting smoking. The program will not interface with the electronic health record, and therefore will be free of additional constraints imposed by HIPAA. Nonetheless, text messaging is not a secure mode of communication. As part of the informed consent process, participants will be informed about the privacy risks associated with text messaging. Participants will also be informed that their interactions with the SmokefreeTXT computer system will be analyzed as a marker for their participation in the program.

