5. Unrelated: Adverse event is clearly not related to investigational agent.

Plan for Grading Adverse Events

The following scale will be used in grading the severity of adverse events noted during the study:

1. Mild adverse event
2. Moderate adverse event
3. Severe unanticipated adverse event resulting inpatient hospitalization or prolongation of existing hospitalization, a persistent or significant disability/incapacity, or a congenital anomaly/birth defect.
4. Life-threatening adverse event
5. Fatal adverse event

Plan for reporting serious AND unanticipated AND related adverse events and anticipated adverse events occurring at a greater frequency than expected to the HIC.

The investigator will report the following types of adverse events to the HIC: a) serious AND unanticipated AND possibly, probably or definitely related events; and b) anticipated adverse events occurring with a greater frequency than expected. These adverse events will be reported to the HIC within 48 hours of it becoming known to the investigator, using Yale HIC Form 6A. Adverse events will be deemed serious in nature if graded as 3 or higher according to the scale in item #4 above.

Plan for Reporting Adverse Events to Co-Investigators

For this study, the following individuals, funding, and/or regulatory agencies will be notified: all co-Investigators listed on the protocol, the HIC, and the National Institutes of Health. The principal investigator ([name]) will conduct a review of all adverse events upon completion of every study subject. The principal investigator and [name] will evaluate the frequency and severity of the adverse events and determine if modifications to the protocol or consent form are required.

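### Severity grade 3 is limited to unanticipated events, so an anticipated event that hospitalises or disables a participant, without being life-threatening or fatal, is non-serious by rule

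*Combined protocol and SAP*

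**What the plan says.** All the operative text is in Section V, item 11 (Data and Safety Monitoring Plan).

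- **Grading scale.** Five grades are introduced as a scale of severity. Grade 2 is "Moderate adverse event". Grade 3 is "Severe unanticipated adverse event resulting inpatient hospitalization or prolongation of existing hospitalization", followed by disability or incapacity and congenital anomaly as alternative outcomes. Grade 4 is "Life-threatening adverse event" and grade 5 is fatal. Only grade 3 mentions whether the event was anticipated.
- **Seriousness.** "Adverse events will be deemed serious in nature if graded as 3 or higher according to the scale in item #4 above". No other definition of serious is given.
- **HIC reporting.** Two classes go to the HIC within 48 hours: (a) "serious AND unanticipated AND possibly, probably or definitely related events" and (b) "anticipated adverse events occurring with a greater frequency than expected".
- **Preamble.** Before the grading scale, the plan says that events of either kind, anticipated or not, may occur and may or may not be serious.
- **Review.** The principal investigator reviews all adverse events as each subject completes. With a colleague, the principal investigator also weighs event frequency and severity to decide whether the protocol or consent form should change.

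**The concern.** Severity, seriousness and expectedness are three different attributes of an adverse event. Grade 3 makes expectedness a condition of a severity grade, and the seriousness rule then carries that condition into the definition of serious. An anticipated event with one of the grade 3 outcomes therefore has no grade that fits it.

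The gap need not be empty. The section on nicotine replacement risks (Section V, item 9) lists nicotine toxicity, with fainting and confusion among its symptoms. It also lists allergic reaction: "Symptoms of an allergic reaction include rash, itching, swelling, dizziness, and trouble breathing". Subjects who have such a reaction after discharge are told to seek medical attention at once. The same section provides for participants who are admitted as inpatients and encourages continued treatment there, so a prolonged stay is a realistic outcome. Half of the participants are assigned to nicotine replacement (8 of 16 arms; 1056 × 8/16 = 528).

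At stake is whether the grade recorded for such an event describes it correctly when the investigators judge severity across the trial.

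**Working it through.** The plan gives no figure on this point, so the check is to apply its rules to each type of event.

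**Inputs** (all from Section V, item 11): the five grade definitions, the rule that serious means grade 3 or higher, and HIC criteria (a) and (b).

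**Step 1. Apply the rules as written.**

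| Event | Grade available | Serious? | HIC (a) | HIC (b) |
|---|---|---|---|---|
| Anticipated; hospitalised or disabled; not life-threatening or fatal | 1 or 2 | No | No | Only if more frequent than expected |
| Unanticipated and severe; hospitalised or disabled | 3 | Yes | Yes, if at least possibly related | Does not apply |
| Anticipated; life-threatening or fatal | 4 or 5 | Yes | No | Only if more frequent than expected |
| Unanticipated; life-threatening or fatal | 4 or 5 | Yes | Yes, if at least possibly related | Does not apply |

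The first row is the anomaly. The outcome is one that grade 3 names, but the event fails grade 3 on expectedness alone and drops to moderate at most.

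**Step 2. Set this against the rest of the plan.** The preamble allows an anticipated event to be serious. Under the scale this is possible only at grades 4 and 5. Criterion (a) lists serious and unanticipated as separate conditions; for a grade 3 event the second is already built into the first and does no work. Both texts assume two attributes where grade 3 has merged them.

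**Step 3. Remove the expectedness condition from grade 3 and reapply.** The first row becomes grade 3 and serious. Its HIC (a) entry stays at no, because (a) itself requires the event to be unanticipated. Its HIC (b) entry is unchanged, because (b) depends on frequency and not on seriousness. The other rows do not move.

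The word therefore changes the grade and the label for one class of event, and no HIC report.

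**The case against.** The strongest case on the other side is that nothing operational follows. The seriousness rule sits in the HIC reporting paragraph, which is its only stated use, and Step 3 shows that reporting is the same with or without the word. Adverse events go to the principal investigator at once, and all are reviewed. The Treatment Service Review also records hospitalisations at 1 and 3 months whatever grade is assigned. All of this stands: no event is hidden.

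Three stronger readings are tempting, and the documents do not support them.

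- *Serious events would go unreported to the HIC.* Criterion (a) would exclude these events under any wording of grade 3.
- *A count of serious events or a stopping rule would be distorted.* The plan specifies no such count or table, and no threshold based on seriousness. The review at least every 6 months, which decides whether the study continues, does not name severity grade as its basis. Event frequency and severity are named only for decisions about the protocol and consent form.
- *The nicotine-related events of most concern would be recorded as mild or moderate.* Life-threatening and fatal events keep grades 4 and 5 whether or not they were anticipated. An allergic reaction with trouble breathing could be grade 4.

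It can also be said that the plan never defines unanticipated. It describes the gum risks as minor and toxicity as passing within hours, so an investigator might call a hospitalising reaction unanticipated in its severity and assign grade 3. This narrows the affected class. It also leaves the grade dependent on an undefined judgement, so two graders could differ on the same event.

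What survives is that a written grading rule, followed literally, gives the wrong grade for a recognisable class of event, and that grade is the natural severity record for a review that looks at severity.

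**Conclusion.** The grade 3 definition is wrong as written and inconsistent with its own plan. An anticipated event that leads to admission, a longer stay or disability, and is neither life-threatening nor fatal, can only be graded 1 or 2 and is non-serious by rule. The effect is a misstated grade and label in the review of event frequency and severity. It is not a loss of data, a missed HIC report or an effect on the efficacy analysis.

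The size cannot be calculated, because the documents give no rate for such events. It is likely small: the trial is assessed as minimal risk. The conclusion assumes that graders follow the text literally, and that listing a risk in the protocol makes a resulting admission anticipated. If graders treat an unusually severe form of a listed risk as unanticipated, the class shrinks further. The point is minor, but worth correcting because the correction is a matter of wording.

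**What to change.** In Section V, item 11:

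1. Delete the word unanticipated from grade 3.
2. Reword grade 3 so that any adverse event with one of the listed outcomes (admission, longer stay, disability or incapacity, congenital anomaly) is grade 3 whether or not it was anticipated. Deleting the one word is not enough, because the word severe could still be read as a further condition.
3. Keep expectedness only in the HIC reporting rule, where criteria (a) and (b) already use it.
4. Correct the reference to item #4 in the seriousness rule. The scale sits under an unnumbered heading, so the rule should point to that heading by name.

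Step 1 changes no HIC report. Step 2 could add one in a narrow case: an unanticipated, related admission that a grader had judged not severe would become serious and so fall under (a). The amendment should say that this is intended.

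The cost is a short wording amendment. Adverse events are already monitored for each subject and hospitalisations are already asked about at 1 and 3 months, so no new data are needed. Sample size and efficacy analysis are untouched.

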Brief negotiated interview (BNI). Brief Negotiated Intervention (BNI) is a manual-guided therapy that is designed to be feasible in the ED setting. The BNI manual for this study is based on one that we used in our previous trial. The purpose of the BNI is to assist patients in recognizing and changing their tobacco use. It combines techniques based on motivational interviewing and a stage-model of change.^{32,46} The main goals of the interview are to decrease subjects' ambivalence about engaging in tobacco dependence treatment and accepting ED-initiated treatment, including NRT, texting, and QL referral.

The BNI will be delivered by a trained research assistant (RA), a bachelor's-level individual, who will audiotape the encounters. Tapes will be reviewed biweekly by the RAs and [name], to assess fidelity to protocol. In our prior work, the BNIs average 10-15 minutes in length. RAs will receive 10 hours of training by [name] in our manualized BNI, and by [name] in nicotine replacement pharmacotherapy. Next, RAs will role-play patient scenarios with [name], followed by 1 week of shadowing an experienced RA performing BNIs on ED patients. We have used these procedures in all prior studies of ED SBIRT.

If, during the BNI or other interactions, the subject discloses to the RA risky behaviors such as suicidality, intimate partner violence, or use of other substances, the RA will notify the treating ED physician.

Nicotine gum and patch, with initial dose applied in the ED. Subjects randomized to NRT will receive 6 weeks of patches (42 count) and gum (300 pieces of 2mg), free of charge. *All NRT will be given to the subject in a small shopping bag.* NRT dosing is tailored to the patient's score on the Heavy Smoking Index.⁴⁷ Patches come in 7, 14 and 21 mg doses. The first patch is applied by an ED nurse during the index visit. This allows us to demonstrate to the subject how to use the patch, its ease of use, and acceptability. It does bypass the traditional model of setting a quit date, although subjects may continue to reduce their tobacco use while using NRT. In our previous study, this approach was accepted enthusiastically by subjects. We employ combination NRT because of its generally greater efficacy than NRT monotherapy in promoting tobacco abstinence.⁴⁸

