Of note, future versions of Epic may contain functionality allowing the provider to send an electronic referral to the state quitline (mentioned at the Epic fall 2014 Users Group Meeting, attended by this proposal's PI). That said, for now we will still have RAs fax the traditional paper referral form to Consumer Wellness Solutions, Inc., the QL vendor for CT.

Post-visit booster call. In our prior studies, intervention subjects received a phone call 2-3 days after enrollment. The purpose of this call is to remind participants that they are enrolled in a trial, ask if they have questions about their treatment, reaffirm contact information, and thank them for participating. We reach about 70% of the subjects. Our experience suggests that these calls add little to the efficacy of the intervention. They do, however, require manpower and support which might be better spent on other activities, like recruiting. We have therefore decided not to perform booster calls in this proposal.

Smoking cessation brochure. In our work, all participants are provided with a brochure that reviews the health hazards of smoking, and provides the phone number for the state quitline. In Connecticut, this brochure is produced by the State Department of Public Health, printed in English and Spanish, and is available in bulk *at low cost*. We believe that distributing this brochure to all study participants is a reasonable maneuver for all subjects. That will not allow

us, of course, to isolate any discrete effect of the brochure on tobacco abstinence. In the parlance of MOST designs, that is known as “aliasing.”⁴³ We believe this is an acceptable approach.

6. Measures. Overview. We will assess a range of pretreatment subject characteristics, process measures and treatment outcomes (Table 2). Baseline assessments are designed to ensure that patients meet eligibility criteria and that important predictor variables are assessed. Process measures include utilization of health care and nicotine dependence treatment services, and adherence to the treatment manual and competence in performing the treatments. Primary outcome measures include tobacco use; secondary measures include engagement in treatment, health care service utilization, and cost indicators. Outcomes will be assessed from multiple sources, including patient self-report of treatment engagement, tobacco use, and objective measures such as Quitline verification regarding patient contact and exhaled carbon monoxide testing.

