Under order of the treating physician, consenting patients will receive their first NRT product (patch and/or gum) in the ED, and a "starter kit" to take home which will include a 6-week supply of medication. Smokers admitted to inpatient units will have their treating physician contacted by the study team, to encourage continuation of pharmacotherapy while in hospital. The study team will follow up with admitted patients who, when, discharged, will receive sufficient medication to fulfill a 6-week course of treatment.

There are minor, non-life-threatening risks associated with using the gum. The subject could use too much, or chew too quickly, which might lead to symptoms of nicotine toxicity. This could also occur if the subject smokes while using the patch or gum. Symptoms associated with nicotine “overdose” include cold sweats, fainting, confusion, and pounding heart. Toxicity resolves in several hours. Cases of nicotine toxicity are extremely rare. In terms of the patch, nicotine continues to enter the bloodstream for several hours after removing it, as it leaches through the skin, so smoking within 12 hours of removing the patch is strongly discouraged. One of the most common side effects of the patch is a localized skin rash due to a reaction to the adhesive on the patch or a reaction to the nicotine. A topical salve (such as 1% hydrocortisone cream) can relieve the discomfort. The second most common side effect is sleep disturbance. This side effect is common in people who use the 24-hour patch. Nicotine can lead to vivid, colorful dreams and difficulty sleeping. For this study, the 24-hour patch will be utilized. Switching to a 16-hour patch might alleviate this problem, but it often can result in nicotine cravings. Other potential side effects of NRT include dizziness, insomnia and abdominal discomfort.

Nicotine gum has a peppery taste, which some participants may find unpleasant. (Note that we mitigate this by using mint-flavored gum.) It may cause a tingling sensation when chewed. During the first few days of using the medication, the participant may experience mouth soreness, jaw muscle aches, increased saliva production, indigestion, or headache. These effects should dissipate over time. There are some risks associated with chewing the gum too fast, in that it can cause lightheadedness, dizziness, hiccups, nausea, vomiting or insomnia. All participants will be asked to notify us if they develop symptoms of too much nicotine in their body.

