- c. Include an appropriate Data and Safety Monitoring Plan. Examples of DSMPs are available here <http://www.yale.edu/hrpp/forms-templates/biomedical.html> for
 - i. Minimal risk
 - ii. Greater than minimal

Data and Safety Monitoring Plan

Monitoring for data integrity and safety will be the responsibility of the investigators and the Yale Human Investigation Committee (HIC). The principal investigator (PI) will be responsible for monitoring the data, assuring protocol compliance, conducting the safety reviews, and the specified frequency of the reviews at a minimum of every 6 months (including when reapproval of the protocol is sought). During the review process, the PI will evaluate whether the study should continue unchanged, require modification/amendment, continue or close to enrollment. Either the PI or the HIC have the authority to stop or suspend the study or require modifications.

Based on our prior work, the risks associated with the proposed study are minimal. We view the risks associated with the combined use of nicotine patch and nicotine gum as minimal. Given the now-established safety and validity of nicotine replacement therapies in our prior work and others', we do not view the proposed studies as high risk. In previous studies by our group, standard doses of NRT such as those proposed in this study were extremely well tolerated. Further, nicotine patch and gum are available over-the-counter, also attesting to their excellent safety profiles.

Although we have assessed the proposed study as one of minimal risk, the potential exists for anticipated and/or unanticipated adverse events, serious or otherwise, to occur since it is not possible to predict with certainty the absolute risk in any given individual or in advance of first-hand experience with the proposed study methods. Therefore, we provide a plan for monitoring the data and safety of the proposed study.

Attribution of Adverse Events

Adverse events will be monitored for each subject participating in the study and attributed to the study procedures / design by the principal investigator ([name]) according to the following categories:

1. Definite: Adverse event is clearly related to investigational agent.
2. Probable: Adverse event is likely related to investigational agent.
3. Possible: Adverse event may be related to investigational agent.

4. Unlikely: Adverse event is likely not to be related to the investigational agent.

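### Non-serious NRT side effects after discharge are counted only if participants volunteer them, and the excess-frequency reporting trigger has no stated expected frequency

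*Combined protocol and SAP*

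**What the plan says.** **Reporting rule.** Section V item 11 (Data and Safety Monitoring Plan) sends two kinds of event to the HIC within 48 hours of the investigator learning of them: (a) events that are serious, unanticipated and at least possibly related, all three together; and (b) "anticipated adverse events occurring with a greater frequency than expected". No expected frequency or threshold is given there or elsewhere.

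**Monitoring.** The same item promises that "Adverse events will be monitored for each subject participating in the study", sets safety reviews at least every 6 months, and says the principal investigator (PI) "will conduct a review of all adverse events upon completion of every study subject". Section V item 9 adds: "All adverse events will be immediately reported to the PI by research staff".

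**How events become known after discharge.** For nicotine symptoms, Section V item 9 (Risks Associated with Nicotine Replacement) states: "All participants will be asked to notify us if they develop symptoms of too much nicotine in their body". The instrument table in Section V item 3, subsection 6 (Measures) lists no adverse-event or side-effect item at either follow-up call. The 2-3 day call used in earlier studies is gone: "We have therefore decided not to perform booster calls in this proposal". The Treatment Service Review (TSR), given at 1 and 3 months, asks about ED visits, hospitalizations and primary care visits, and adds questions on cessation medication use. It is classed as a process measure.

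**Smoking while on NRT.** On nicotine toxicity, item 9 says: "This could also occur if the subject smokes while using the patch or gum". The descriptions of the NRT component (Section V item 3, subsection 5, and Section VI.A.2) set no quit date, "although subjects may continue to reduce their tobacco use while using NRT".

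**The concern.** Trigger (b) compares an observed frequency with an expected one, and the plan secures neither side. Rash, sleep disturbance, excess-nicotine symptoms, gum effects and allergic reaction are all listed as risks, so they are anticipated. As worded, route (a) excludes them and only (b) can carry them to the HIC.

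Volunteered reports give a count with an unknown capture rate. A low count may mean good tolerability or merely that nobody was asked. The PI is to judge the frequency and severity of events and decide whether the protocol or consent form needs changing, and that judgement would rest on such counts. What is at stake is the safety monitoring of NRT. The primary endpoint and its analysis are not affected.

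**Working it through.** The documents give no adverse-event count, rate or threshold, so there is no stated figure to reproduce. The check sets the provisions side by side and then does some illustrative arithmetic.

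**1. What each route can pick up**

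| Route | What it captures | What it leaves open |
|---|---|---|
| Per-subject monitoring (V.11) | All events, in principle | No question, form or interval |
| Staff report to the PI (V.9) | Events staff already know of | How staff learn of them after discharge |
| Participant notification (V.9) | Excess-nicotine symptoms, if volunteered | Capture rate unknown |
| TSR at 1 and 3 months (V.3) | Events leading to an ED visit, admission or primary care visit | No stated link to grading, attribution or the 48-hour report; misses effects for which no care is sought |
| Follow-up of admitted patients (V.9) | Contact until discharge | Described as securing the medication supply |

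For a non-serious effect at home that does not lead to care, participant notification is the only stated route.

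**2. Timing.** The supply is 42 patches, one per day. A day-30 call covers 30/42 = 71% of the course. A day-90 call falls 90 − 42 = 48 days after the supply ends.

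**3. Participants assigned to NRT.** Each component goes to half of 1056: 1056/2 = 528.

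**4. Illustrative number smoking while using NRT.** Inputs: 14/30 abstinent at 1 month in the texting pilot's intervention arm, which had a 4-week supply (V.3, Preliminary Studies 2), and 75% self-reported medication use among non-abstinent intervention subjects in the earlier two-arm trial (Preliminary Studies 1, Table 1).

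- Not abstinent: (30 − 14)/30 = 53.3%, exact 95% CI 34.3% to 71.7%.
- Smoking and using NRT: 0.533 × 0.75 = 40%; 0.40 × 528 ≈ 211.
- Range from the CI: 0.343 × 0.75 × 528 ≈ 136 to 0.717 × 0.75 × 528 ≈ 284, roughly 135 to 285.

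This combines two studies and assumes that smoking and NRT use overlapped in time. It counts exposure, not events.

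**5. What incomplete capture does.** The documents give no capture share c and no event rate p, so both are assumed here.

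- Chance of at least one report among 528 is 1 − (1 − pc)^528. With p = 1% (5.3 events expected) it is 99.5% at c = 100%, 73% at c = 25% and 41% at c = 10%.
- If no event is reported, the one-sided 95% upper bound on the rate at full capture is 1 − 0.05^(1/528) = 0.57%. Dividing by c gives about 1.1% at c = 50%, 2.3% at 25% and 5.7% at 10%.

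So low capture weakens the trigger and makes a quiet record hard to interpret. It does not stop the trigger from ever being met.

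**The case against.** The strongest reply is that monitoring is promised for every subject, staff must report events at once, the PI reviews safety at least every 6 months, and the TSR actively asks about care at both calls. The instrument table is not a call script, so a missing row does not prove that no question is asked. The protocol calls nicotine toxicity very rare and short-lived, reports that NRT was well tolerated in the group's earlier studies, notes that it is sold over the counter, and rates the trial as minimal risk.

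Much of this stands, and it rules out several stronger readings that a reader might infer:

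- **That every adverse event depends on volunteering.** The TSR gives events leading to care a structured route, and reactions in the ED can be seen by staff.
- **That the trigger can never fire.** Volunteered, observed and TSR-detected events can accumulate.
- **That most NRT participants will smoke while using it.** The illustrative share is 40%. The earlier trial's 3-month result might seem to give more, (386 − 47)/386 × 0.75 × 528 ≈ 348, but abstinence was measured about 48 days after a 6-week supply would have ended, so it does not describe smoking on NRT.
- **That the acceptability criterion for keeping NRT fails.** Section V item 12 (Qualitative analysis) judges it by interviews and Likert items, not by an event rate.
- **That the passages on smoking during NRT flatly contradict each other.** One describes a risk; the others say that participants may still be cutting down. They pull apart in emphasis and should be reconciled.

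The reply does not supply a method for eliciting non-serious events, a link from the TSR to event review, or an expected frequency.

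**Conclusion.** The point holds in limited form. For non-serious NRT effects after discharge, trigger (b) has no systematic numerator, and for all anticipated events it has no stated reference frequency. It cannot be reliably applied as written, although reported events could still prompt it. This rests on the provisions themselves and needs no assumption about event rates.

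The number exposed is illustrative: about 211 of 528, roughly 135 to 285, from a pilot arm of 30 combined with medication use from another trial, assuming that smoking and NRT use overlap. The interval reflects only the sampling error of the pilot figure. No figure in the documents measures concurrent use.

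Given the minimal-risk rating, this is an inexpensive improvement to safety monitoring that should be made. It is not a threat to the trial's efficacy conclusions.

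**What to change.** 1. Add a short fixed checklist of the events already named in Section V item 9 (skin reaction, sleep disturbance, excess-nicotine symptoms, gum effects, allergic reaction) to the existing 1- and 3-month calls in all 16 arms. Tabulate it by NRT on/off at each 6-month review, with the number asked as denominator.
2. State a reference frequency for trigger (b). The NRT-off arms can supply it only for symptoms not specific to the product, such as sleep disturbance, dizziness or headache. Patch-site and gum effects need a stated expected rate, because participants without study patches or gum would show almost none and known effects would exceed that reference almost automatically.
3. Pass TSR-reported hospitalizations and ED visits to the PI for grading and attribution. Keep the 48-hour report for those meeting the existing HIC criteria; in a population recruited in an ED it should not start for every visit.
4. Reconcile the wording on smoking while using NRT between Section V item 9 and the two descriptions of the NRT component. Which wording should prevail is for the investigators.

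Cost: a few minutes on calls already scheduled, one table per review, PI time for TSR-reported visits, and more minor events logged. No new visits or procedures are needed.
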